2.2 Secondary Objective(s)

• To quantitate Tc 99m tilmanocept anatomic localization based on SPECT/CT imaging of hands and wrists in HCs and joints with RA-involved inflammation.

2.3 Safety Objective(s)

• To evaluate safety through the examination of AE incidence and changes over time in laboratory tests, vital signs, and physical examination findings.

3 INVESTIGATIONAL PLAN

3.1 Overall Study Design and Plan

This is a prospective, open-label, multicenter, single-dose study designed to develop a normative database of TUV_{joint} in HCs and to assess the feasibility of qualitative and quantitative SPECT/CT assessments in HCs and subjects with active RA following Tc 99m tilmanocept administration. Subjects will be enrolled in 1 of 2 study arms (Table 4) with distinct study procedures in accordance with Arm-specific eligibility requirements.

Arm	n	Subjects	Evaluation(s)
1	120 HCs	HC subjects clinically free of any inflammatory disease and/or joint pain	Planar image of bilateral hands/wrists
2	5 HCs 10 RA	HC subjects clinically free of any inflammatory disease and/or joint pain and subjects with clinically diagnosed active RA who have been on stable anti-rheumatic therapy	Planar image of bilateral hands/wrists SPECT/CT of bilateral hands/wrists

Table 4 Study Arms

3.1.1 Arm 1: No Inflammatory and/or Joint Disease (HC Subjects)

3.1.1.1 Description of Patient Population

This arm will be comprised of 120 HCs who are deemed to be clinically free of inflammatory disease(s) and/or arthropathies and clinically free of joint pain for at least 28 days prior to the consent date. These subjects will not receive any anti-inflammatory treatment(s) (including NSAIDs) during study participation and will not have taken any such drugs at least 28 days prior to the consent date. All other concomitant medications (for non-inflammatory conditions) will have been maintained at a stable dose for at least 28 days prior to consent.

3.1.1.2 Overview of Study Procedures

Subjects in this arm will have a total of two on-site visits and one telephone safety assessment. The maximum possible study duration for these subjects will be 39 days.

3.1.1.3 Justification for Population

The reason for the inclusion of this study population is to establish mean and variance for TUV_{joint} values in HCs to develop a normative database to which the inflamed joints of subjects with active RA can be compared. By determining the upper limit of normal (ULN) for average anterior or posterior TUV_{joint} for right and left joints of the bilateral hands and wrists, these

assessments can be further investigated for their utility in providing clinically meaningful reference data for symptomatic individuals presenting to the clinic.

3.1.2 Arm 2: HCs and RA Subjects on Stable Anti-Rheumatic Therapy

3.1.2.1 Description of Patient Population

This arm will include five (5) HCs who are deemed to be clinically free of inflammatory disease(s) and/or arthropathies and clinically free of joint pain for at least 28 days prior to the consent date. These subjects will not receive any anti-inflammatory treatment(s) (including NSAIDs) during study participation and will not have taken any such drugs at least 28 days prior to the consent date. All other concomitant medications (for non-inflammatory conditions) will have been maintained at a stable dose for at least 28 days prior to consent.

This arm will also include ten (10) subjects with clinically diagnosed active RA on stable antiinflammatory and/or anti-rheumatic therapy. All subjects' RA diagnoses will be moderate to severe in accordance with a 2010 ACR/EULAR score of 6 or higher. All subjects receiving traditional DMARDs must have been on therapy for \geq 90 days and at a stable dose for \geq 30 days prior to the first imaging visit; all subjects receiving bDMARDs must have been on therapy for at least 60 days prior to the first imaging visit; and all subjects receiving NSAIDs and/or oral corticosteroids must have been on therapy for at least 28 days prior to the first imaging visit (Table 7).

Table 5	Inclusion Criteria Treatment Windows for Recent or Concomitant
	RA-specific Treatments

Drug Class	Window
Traditional DMARDs	On the rapy ≥ 90 days and at a stable dose ≥ 30 days prior to the imaging visit (Day 0)
bDMARDs	> 60 days prior to the imaging visit (Day 0)
JAK inhibitors	> 60 days prior to the imaging visit (Day 0)
NSAIDs/Corticosteroids	\geq 28 days prior to the imaging visit (Day 0)

3.1.2.2 Overview of Study Procedures

Subjects in this arm will have a total of two on-site visits and one telephone safety assessment. The maximum possible study duration for these subjects will be 39 days.

3.1.2.3 Justification for Population

The reason for the inclusion of this study population is to assess the feasibility of qualitative and quantitative SPECT/CT assessments following Tc 99m tilmanocept administration. HCs will provide control data to which data from RA subjects on stable therapy can be compared. Planar imaging from these subjects will be utilized for comparison to SPECT/CT results and will be pooled with data from this and previous Navidea RA trials for TUV evaluations.

3.2 **Protocol Adherence**

Strict adherence to all specifications outlined in this protocol is required for all aspects of the study conduct; the investigator may not modify or alter the procedures described in this protocol. If protocol modifications are necessary, all alterations that are not solely of an administrative nature require a formal protocol amendment for the involvement of Institutional Review Board(s) (IRB(s)).

If an investigator has deviated from the protocol in order to eliminate an immediate hazard to subjects or for other inevitable medical reasons, the investigator shall document all such deviations, including the reasons thereof, and submit the document to the sponsor and the IRB as applicable.

3.3 Study Duration(s)

The maximum possible study duration for Arm 1 or 2 subjects is 39 days.

4 STUDY POPULATION

4.1 Study Arms

The study population will be comprised of HCs and subjects with clinically diagnosed active RA on stable anti-rheumatic therapy. Subjects will be enrolled in 1 of 2 study arms (Table 6):

Arm	n	Subjects	Evaluation(s)
1		HC subjects clinically free of any inflammatory disease and/or joint pain	Planar image of
	120 HCs		bilateral
			hands/wrists
2			Planar image of
		HC subjects clinically free of any	bilateral
	5 110	inflammatory disease and/or joint pain and	hands/wrists
	5 HCs	subjects with clinically diagnosed active RA	
	10 KA	who have been on stable anti-rheumatic	SPECT/CT of
		therapy	bilateral
		1.0	hands/wrists

Table 6Study Arms

4.2 Eligibility

All inclusion/exclusion criteria must be verified before any subject is considered eligible for enrollment and for administration of Tc 99m tilmanocept and imaging (Day 0 procedures). Subjects will be considered enrolled once injected with Tc 99m tilmanocept (Day 0). Written and dated (with time-noted) informed consent will be obtained from all subjects. A subject who withdraws consent prior to receiving Tc 99m tilmanocept injection on Day 0 will be considered a screen failure.

4.2.1 Inclusion Criteria

ALL SUBJECTS

- 1. The subject has provided written informed consent with HIPAA authorization before the initiation of any study-related procedures.
- 2. The subject has agreed to not engage in any diet, lifestyle, or medication changes until study completion.

HEALTHY CONTROL SUBJECTS

- 3. The subject is 30 years of age or greater at the time of consent.
- 4. The subject is deemed to be clinically free of any inflammatory disease(s), autoimmune disease(s), or arthropathies and has not experienced joint pain for at least 28 days prior to the consent date.

- 5. The subject is not currently on anti-inflammatory drugs (including NSAIDs) and has not taken any anti-inflammatories for at least 28 days prior to the consent date.
- 6. For all ongoing concomitant medications, the subject has maintained a stable dose for at least 28 days prior to the consent date.

CLINICALLY DIAGNOSED ACTIVE RA SUBJECTS

- 3. The subject is at least 18 years of age and was ≥ 18 years of age at the time of RA diagnosis.
- 4. The subject has moderate to severe RA as determined by the 2010 ACR/EULAR Classification Criteria (score of $\geq 6/10$).
- 5. The subject has a DAS28 of \geq 3.2 (includes the ESR test and VAS).
- 6. If the subject is receiving traditional DMARDs, they have been on therapy for ≥ 90 days and at a stable dose for ≥ 30 days prior to the imaging visit (Day 0).
- 7. If the subject is receiving bDMARD or JAK inhibitor therapy, they have been at a stable dose > 60 days prior to the imaging visit (Day 0).
- 8. If the subject is receiving NSAIDs or oral corticosteroids, the dose has been stable for ≥ 28 days prior to the imaging visit (Day 0). The corticosteroid dose must be ≤ 10 mg/day of prednisone or an equivalent steroid dose.

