9.5.3 Analysis of Efficacy Variables

All efficacy analyses will be conducted on both the ITD and PP populations. The ITD population will be the primary analysis set.

9.5.3.1 Primary Endpoint Arm 1

The distribution of TUV_{joint} in HC subjects will be summarized with descriptive statistics: mean, standard deviation, n, minimum, maximum, and median per reader, joint, and view. The 5 and 95 percentiles will be estimated with quantile regression fitting an intercept as a fixed term. The lower and upper limits of normal TUV_{joint} will be determined using non-parametric confidence intervals and kernel density-based confidence intervals.

9.5.3.2 Primary Endpoint Arm 2

Localization of tilmanocept in the hands and wrists will be summarized with frequency counts and percentages by reader and joint.

9.5.3.3 Secondary Endpoint Arm 1

Normal quantile plots will be provided per joint and reader, along with the *p*-value for the Shapiro-Wilk test of Normality.

9.5.3.4 Secondary Endpoints Arm 2

SUV will be calculated and summarized on both a per-joint and a total of all joints with summary statistics: mean, standard deviation, n, minimum, maximum, and median.

The predictive value of planar scans for SPECT/CT qualitative findings will be summarized per joint and reader with a crosstabulation and the uncertainty coefficients for row | column, column | row, and symmetric. The planar result will be deemed "positive" (i.e., inflamed) if $TUV_{joint} > 95$ percentile of the reader results for the same joint in Arm 1. Otherwise, the planar result will be deemed "negative".

Additional efficacy analyses may be described in the NAV3-35 Statistical Analysis Plan (SAP).

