Appendix 2 2010 ACR/EULAR Criteria

	Score
Target population (Who should be tested?): Patients who	
1) Have at least 1 joint with definite clinical synovitis (swelling)*	
2) With the synovitis not better explained by another disease ⁺	
Classification criteria for RA (score-based algorithm: add score of categories A-D;	
A score of $\geq 6/10$ is needed for classification of a patient as having definite RA);	
A. Joint involvement§	
1 large joint	0
2-10 large joints	1
1-3 small joints (with or without involvement of large joints)	2
4- 10 small joints (with or without involvement of large joints)	3
> 10 joints (at least 1 small joint)**	5
B. Serology (at least 1 test result is needed for classification) ^{‡‡}	
Negative RF and negative ACPA	0
Low-positive RF or low-positive ACPA	2
High-positive RF or high-positive ACPA	3
C. Acute-phase reactants (at least 1 test result is needed for classification) ‡‡	
Normal CRP and normal ESR	0
Abnormal CRP or abnormal ESR	1
D. Duration of symptoms§§	
< 6 weeks	0
≥ 6 weeks	1

* The criteria are aimed at classification of newly presenting patients. In addition, patients with erosive disease typical of rheumatoid arthritis (RA) with a history compatible with prior fulfillment of the 2010 criteria should be classified as having RA. Patients with longstanding disease, including those whose disease is inactive (with or without treatment) who, based on retrospectively available data, have previously fulfilled the 2010 criteria should be classified as having RA.

[†] Differential diagnoses vary among patients with different presentations, but may include conditions such as systemic lupus erythematosus, psoriatic arthritis, and gout. If it is unclear about the relevant differential diagnoses to consider, an expert rheumatologist should be consulted.

‡ Although patients with a score of < 6/10 are not classifiable as having RA, their status can be reassessed and the criteria might be fulfilled cumulatively over time.

§ Joint involvement refers to any swollen or tender joint on examination, which may be confirmed by imaging evidence of synovitis. Distal interphalangeal joints, first carpometacarpal joints, and first metatarsophalangeal joints are excluded from assessment. Categories of joint distribution are classified according to the location and number of involved joints, with placement into the highest category possible based on the pattern of joint involvement.

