# 7.0 List of Analysis Tables, Figures and Listings

Table No.	Table Title	Included in Final Tables	Shown in Appendix B
1	Subject Disposition by Study Arm	X	X
2	Demographics and Baseline Data Summary Statistics by Arm – Continuous Variables (Safety Population)	Х	Х
3	Demographics and Baseline Data Summary Statistics by Arm – Categorical Variables (Safety Population)	Х	Х
4	Summary of Study Drug Administration by Arm (Safety Population)	Х	Х
5	Summary of TUV joint on both Arms Per Reader, Joint, and View (ITD population)	Х	Х
6	Summary of TUV joint on both Arms Per Reader, Joint, and View (PP Population)	Х	
7	Summary of SUV on Arm 2 per Joint and a Total of All Joints (ITD population)	Х	Х
8	Summary of SUV on Arm 2 per Joint and a Total of All Joints (PP Population)	Х	
9	Normal Range of TUV joint for the Three Blinded Readers in All Arm 1 and 2 Healthy Control Subjects (ITD Population)	Х	Х
10	Normal Range of TUV joint for the Three Blinded Readers in All Arm 1 and 2 Healthy Control Subjects (PP Population)	Х	
11	Correlation Between TUV joint and Age and BMI – All Arm 1 and 2 Healthy Control Subjects (ITD Population)	Х	Х
12	Correlation Between TUV joint and Age and BMI – All Arm 1 and 2 Healthy Control Subjects (PP Population)	Х	
13	Frequency Counts and Percentage of Localization in SPECT/ CT Imaging in RA Subjects (ITD Population)	Х	Х
14	Frequency Counts and Percentage of Localization in SPECT/ CT Imaging in RA Subjects (PP Population)	Х	
15	Shapiro-Wilk P-Value for Normality Test for TUV joint Data – All Arm 1 and 2 Healthy Control Subjects (ITD Population)	Х	Х
16	Shapiro-Wilk P-Value for Normality Test for TUV joint Data – All Arm 1 and 2 Healthy Control Subjects (PP Population)	Х	
17	Predictive Value of Planar Scans for SPECT/CT Per Joint and Reader (ITD Population)	Х	Х
18	Predictive Value of Planar Scans for SPECT/CT Per Joint and Reader (PP Population)	Х	
19	Number and Percentage of Subjects with TEAEs (Safety Population)	Х	Х
20	Summary of TEAEs (Safety Population)	Х	Х
21	Number and Percentage of Subjects with TESAEs (Safety Population)	Х	Х
22	Number and Percentage of Subjects With TEAEs by Severity Grade (Safety Population)	Х	Х
23	Number and Percentage of Subjects With TEAEs by Level of Relationship to Tc 99m Tilmanocept (Safety Population)	Х	Х
24	Number and Percentage of Subjects With TEAEs by Level of Relationship to Procedure (Safety Population)	Х	

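### Arm 2 sets out to quantify SPECT/CT uptake in inflamed RA hand and wrist joints, but SUV is summarised over all RA joints and never by inflamed status

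*Protocol*

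**What the plan says.** - Objective (Protocol 2.2, repeated in SAP 1.0): quantify tracer localisation from "SPECT/CT imaging of hands and wrists in HCs and joints with RA-involved inflammation". The RA side is defined by joint, not by subject.
- Endpoint (Protocol 9.3, SAP 4.1.2): quantitative SPECT/CT evaluation of the hand and wrist synovial spaces in HCs and RA subjects. Here the RA side is defined by subject.
- Analysis (Protocol 9.5.3.4, SAP 4.2.2): "SUV will be calculated and summarized on both a per-joint and a total of all joints". The Table 7 shell in SAP Appendix B has HC-2 and RA blocks, one row per joint and a total row. It has no row or column for inflamed status.
- RA entry (Protocol 4.2.1): "The subject has moderate to severe RA as determined by the 2010 ACR/EULAR Classification Criteria", with a score of at least 6 out of 10, and a DAS28 of at least 3.2. No inclusion or exclusion criterion asks for an involved hand or wrist joint, although only hands and wrists are imaged.
- Inflamed joints elsewhere: SAP 2.5 calls an RA joint inflamed when planar TUV exceeds the upper limit of normal in either view, and sums only those joints into the global TUV. Table 17 cross-tabulates planar-positive joints against qualitative SPECT/CT by reader and joint. The DAS28 result for each joint is only listed (Data Listing 18).

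**The concern.** The objective and the only table that could answer it describe different sets of joints. RA subjects are on stable therapy, and nothing in the plan makes all 22 imaged joints inflamed. Each RA row of Table 7 is therefore a mixture of inflamed and quiet joints, and its mean is pulled toward the healthy-control value. A small RA-HC difference in SUV could mean that SPECT/CT quantitation separates inflamed joints poorly, or that few of the averaged joints were inflamed. Table 7 cannot tell these apart. A subject whose disease lies wholly outside the hand and wrist would add to the mixing, and the entry criteria allow such a subject.

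**Working it through.** The Arm 2 size (5 HCs, 10 RA) is given without alpha, power, effect or precision target, so there is no sample-size figure to reproduce. Two scale checks agree with the plan: the Appendix 2 maximum is 5 + 3 + 1 + 1 = 10, and 2 wrists + 10 MCP + 10 PIP = 22 imaged joints, which leaves 28 - 22 = 6 DAS28 joints (shoulders, elbows, knees) outside the hand and wrist.

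**Step 1. Can both RA entry scores be met with no involved hand or wrist joint?**

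ACR/EULAR (Protocol Appendix 2), with both knees swollen and tender:
- "2-10 large joints": 1
- "High-positive RF or high-positive ACPA": 3
- abnormal CRP or ESR: 1
- symptoms for 6 weeks or more: 1
- total 1 + 3 + 1 + 1 = 6, which meets the threshold exactly.

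This is the only one of the 12 serology, acute-phase and duration combinations that reaches 6 from large joints alone. Metatarsophalangeal joints 2 to 5 also count as small joints, so foot disease opens further routes: with 2, 3 or 5 joint points, 4, 7 or 11 of the 12 combinations reach 6.

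DAS28 (Protocol 8.3.2), same subject, TJC = 2, SJC = 2, with ESR = 15 and VAS = 20 chosen for illustration:

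0.56 x sqrt(2) + 0.28 x sqrt(2) + 0.7 x ln(15) + 0.014 x 20 = 0.79 + 0.40 + 1.90 + 0.28 = 3.36 (from unrounded terms), above 3.2.

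So both scores can be met with 0 of 22 imaged joints clinically involved. Each such subject would supply 22 of 10 x 22 = 220 RA joint observations, or 10%.

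**Step 2. How much does pooling dilute the SUV contrast?**

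Let m be the mean SUV of uninflamed joints, m + d the mean of inflamed joints, and f the inflamed share in an RA row. Assume that uninflamed RA joints behave like HC joints. Then

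RA row mean - m = (1 - f) x m + f x (m + d) - m = f x d.

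The row keeps a fraction f of the true excess. The documents give no f, so a range is shown with the inflamed joints expected among the 20 RA joints of a bilateral site:

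| f (assumed) | Excess kept | Inflamed joints of 20 |
|---|---|---|
| 0.1 | 10% | 2 |
| 0.3 | 30% | 6 |
| 0.5 | 50% | 10 |
| 0.7 | 70% | 14 |

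**Step 3. Would split rows hold enough joints?**

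At a one-sided site there are 10 RA joints. If joints were independent, the chance of no inflamed joint there is (1 - f)^10: 35% at f = 0.1 and 2.8% at f = 0.3. Some per-site strata may therefore be empty or nearly so, while a split pooled over joint types has 220 joints to divide (66 expected inflamed at f = 0.3).

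**The case against.** The best defence is that Table 7 reports what the endpoint asks for, SUV in HCs and RA subjects by anatomical joint, in a small descriptive feasibility arm. That is correct for the endpoint. It leaves the objective, which names inflamed joints, without a matching SUV summary.

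Four further points limit the concern:
- A reader might infer that the plan never isolates inflamed joints at all. It does, through the planar flag in SAP 2.5 and through Table 17. Table 17 also helps to interpret a low qualitative localisation rate, because it separates planar-positive from planar-negative joints. What is missing is the link to SUV.
- DAS28 alone reaches 0.7 x ln(40) + 0.014 x 50 = 3.28 with no tender or swollen joint, and a reader might infer that such a subject is eligible. With no involved joint anywhere, current ACR/EULAR scoring gives at most 0 + 3 + 1 + 1 = 5, and Appendix 2 also asks for a joint with clinical synovitis. Entry would need joints outside the 28-joint count or the retrospective route in the Appendix 2 footnote.
- The knee-only route is narrow, and the documents do not say how often RA subjects without hand disease would enrol. Most of the dilution comes from f, which is below 1 in almost any RA cohort.
- Protocol 1.2.4.1 and 1.2.4.2 report that tracer localisation and swollen or tender joints did not agree well in the earlier studies. Clinical status alone is therefore a weak definition of the target joints. This is a reason to define the target in advance, not a reason to pool.

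**Conclusion.** The gap is real but specific: SUV is not summarised by inflamed status, so the secondary objective as worded has no matching SPECT/CT quantitation. Under the mixture model each RA row shows about f of the true inflamed-joint excess, 30% at f = 0.3 and 50% at f = 0.5. This assumes that uninflamed RA joints resemble HC joints; f itself is not in the documents. The entry criteria do not ensure an involved hand or wrist joint, but that is a contributing factor of unknown frequency, and the pooling problem stands without it.

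The documents do not support the stronger conclusions that Arm 2 will enrol RA subjects with nothing to image, or that a particular entry rule is needed. Requiring a minimum of hand or wrist involvement would remove little of the dilution while narrowing recruitment to a 10-subject group. Arm 1 and its normal limits are not affected.

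**What to change.** In the SAP, before SUV results are seen:

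1. Define what counts as RA-related inflammation in a joint. Use the planar flag already in SAP 2.5, and state which limit applies: SAP 2.5 sets up a 95% prediction interval, while SAP 4.2.2 uses the 95th percentile. The flag is reader-specific and the Table 7 shell has no reader column, so say how readers are handled.
2. In Tables 7 and 8, split the RA rows into inflamed and not inflamed by that flag, beside the unsplit HC-2 rows.
3. Add a second display split by screening swollen or tender status from the joint count behind Data Listing 18. The two markers were not concordant in earlier studies. The planar flag also selects joints for high uptake of the same tracer, so part of the SUV contrast it shows is built in; the clinical split does not have that feature.
4. Where per-site strata are sparse, pool across joint types and show the number of joints and subjects in each row.

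The sponsor should also reconcile the RA entry criteria with the hand and wrist objective; no entry rule is proposed here.

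The cost is a definition and a few table rows from data already being collected. The drawback is small cell counts with 10 RA subjects, so the split rows should be read as descriptive.

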4.2.2 Exclusion Criteria

- 1. The subject is pregnant or lactating.
- 2. The subject size or weight is not compatible with imaging per the investigator.
- 3. The subject is currently receiving radiation therapy or chemotherapy or has received radiation therapy or chemotherapy in the past six months.
- 4. The subject has had a finger, hand, and/or wrist amputation or hand or wrist joint arthroplasty.
- 5. The subject has renal insufficiency as demonstrated by a glomerular filtration rate of < 60 mL/min.
- 6. The subject has hepatic insufficiency as demonstrated by ALT (alanine aminotransferase [SGPT]) or AST (aspartate aminotransferase [SGOT]) greater than 2 times the upper limit of normal.
- 7. The subject has any severe, acute, or chronic medical conditions and/or psychiatric conditions and/or laboratory abnormalities that would impart, in the judgment of the investigator, excess risk associated with study participation or study drug administration that would deem the subject inappropriate for study participation or compromise the safety of the subject or the quality of the data.
- 8. The subject has any unstable medical illnesses, including hepatic, renal, gastroenterologic, cardiovascular (including ischemic heart disease), endocrinologic, neurologic, immunologic, or hematologic disease.

- 9. The subject has a known allergy to or has had an adverse reaction to dextran exposure.
- 10. The subject has received an investigational product within 30 days prior to Tc 99m tilmanocept administration (Day 0).
- The subject has received intra-articular corticosteroid injections ≤ 8 weeks prior to Tc 99m tilmanocept administration (Day 0).
- 12. The subject has received any radiopharmaceutical within 7 days or 10 half-lives prior to Tc 99m tilmanocept administration (Day 0).
- 13. **Healthy Controls only:** The subject has a positive rheumatoid factor and an elevated ESR or CRP.

